Medication will not be increased above 600mg/day at this visit. However, if medication adjustments are still needed, an additional blood draw for a serum lithium level may be scheduled with Exam One, with an additional blood draw kit shipped to the participant in advance, OR the participant may be scheduled to complete the visit in clinic.

The following assessments will be completed at the week 10 visit:

- Concomitant Medications
- CGI Behavior (CGI-S, CGI-C)
- CGI Global (CGI-S, CGI-C)
- NPI
- Stereotypic and ritualistic behaviors
- TESS
- Medication compliance (the study partner will be asked to count on camera the number of pills remaining in the bottle they used for the first two weeks to ensure correct dosing. 14 pills should remain in the 2nd bottle if the medication has been taken for 14 days at 450mg/day).

Completed by ExamOne (IF NECESSARY):

- Vital signs
- Serum lithium level
- Safety labs

The week 10 visit is estimated to take 50-60 minutes on average.

Color-codes	
Coordinator	
Physician	
Time	Assessment
10 minutes	TESS, Concomitant Meds, CGI, with
	Patient and Caregiver.
30 minutes	NPI with Caregiver
10 minutes	Medication compliance review

Vital signs and blood draw will be scheduled separately and completed by the Exam One mobile phlebotomy team, who will ship samples directly to the CALM lab for processing.

Week 12 Visit

At CUMC, unblinding by the study physician will occur after all week 12 measures and procedures have been completed.

The following assessments will be completed at the week 12 visit:

- Concomitant Medications
- CDR
- CGI Behavior (CGI-S, CGI-C)
- CGI Global (CGI-S, CGI-C)
- NPI
- Stereotypic and ritualistic behaviors
- TESS
- Zarit Caregiver Burden Interview
- Vital signs
- blood specimens collected
- ECG
- protocol exit form
- Medication compliance: kit collection. An additional 4 bottles (128 pills) should have been used since the week 8 visit if the bottle if the medication has been taken for 28 days at 600mg/day).

Blinding: Lithium/sham levels procedures

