- Review next steps: 1) confirmation of eligibility after lab results are returned, 2) shipment of study drug and phone call once it arrives (it is good to go over the starting dosing schedule / potential side effects at this time as well), 3) scheduling of week 2 virtual visit 2 weeks after study drug arrives.

Post-visit:

- Obtain any missing signatures
- □ Score cognitive testing & caregiver forms
- □ Fill in any incomplete documents (e.g. inclusion/exclusion) to the best of your ability
- Check CALM website for posting of testing results
 - o sac-cu.org on internet explorer-- download "detailed results"
 - Copy the results into the "Safety Labs Template" file in dopamine>Lithium in FTD>Biological Samples, convert the results to numbers in excel (out of range results will highlight in pink), & print
- □ Obtain physician signature on lab results & ECG
- Prepare pharmacy referral form to send to pharmacy once inclusion/exclusion criteria met (get physician signature & scan). See "Randomization" section for sample email.
- Organize forms in new participant binder or folder
- □ Enter data on REDCap- you will need to use both "screening" and "week 0" tabs

- □ Complete MHLS form (if surrogate signed consent) & email to IRB, print and put in participant binder / regulatory binder, and mail or fax to the NY office of Legal Services.
- □ Complete **study drug issue/return log** once the participant receives the drug kit. For this log, note that each kit contains 12 medication bottles. Each bottle contains 28 pills and is labeled by week (#1-12). Each pill is 150mg of study drug.
 - Under "Study Drug Bottle ID", put "LF1XX Week(s) X" to denote the bottle you are instructing the participant to use up until the next study visit (in this case it would be LF1XX Week 1).
 - For number of pills dispensed, indicate the number of pills in the bottle(s) you are instructing the participant to use. You will refer to these bottles at the following visit when you fill in information for study drug returned, and will include the pills remaining in the previously specified bottle as "pills returned".
 - For dose recommended, write the daily dose in mg.
 - It is important to instruct the participant to begin a new bottle after each study visit, regardless of whether pills remain in the old bottle. While taking 150-300mg/day, participants will only need one bottle between visits, but when taking 450-600mg/day, they will need two.

Week 2

Pre-visit:

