- □ If no contradictions per study clinician, instruct participant/study partner to increase dose to 450mg/day (one pill mornings, two pills evenings), using two new bottles.
- □ Schedule Week 6 visit with participant for 2 weeks after their week 2 visit.
- Obtain clinician signature on REDCap study drug issue/return log resolve any missing data from clinician forms

Week 6

Pre-visit:

Schedule an at-home blood draw via ExamOne, to occur as close to the virtual visit as possible. Notify the CALM lab of the anticipated date of this visit so they can expect the shipment. Remind study partner not to give medication dose morning of blood draw.

- □ Create zoom link & send along with date/time of visit & visit schedule to the study partner
- □ Send a calendar invitation to the study physician. In the calendar invitation, include:
 - o Zoom link
 - Links to clinician forms within REDCap for the correct subject/week
 - List of clinician forms: Treatment emergent symptoms, CGI-Severity, CGI-Change
 - Current subject medication dose, anticipated dose change after visit, & any other relevant information

During visit:

- □ Complete medication compliance check: have study partner count pills remaining in the bottle they have been using. Each bottle contains 28 pills, so calculate the number of pills that should be remaining based on dose & time since the last visit.
- On REDCap, complete the following forms with the study partner:
 - Visit registry, concomitant meds, NPI, Stereotypic/Ritualistic behaviors, study drug issue/return log

Post-visit:

- Following the at-home blood draw, complete a Serum Sham Lithium Level Form (dopamine>Lithium in FTD>Serum-Sham Lithium Levels) and send it to [name], who will send the form to [name] along with the REAL serum lithium level (once it is available on CALM). [name] will then complete the form and send it back to [name], who will send it to you. Save the signed form in a unique subject folder in dopamine>Lithium in FTD>Serum-Sham Lithium Levels.
- If no contradictions per study clinician, AND serum lithium/sham level is within the target window, instruct participant/study partner to increase dose to 600mg/day (two pills mornings, two pills evenings), using two new bottles.
- Obtain clinician signature on REDCap study drug issue/return log, resolve any missing data from clinician forms, fill out serum-sham lithium level REDCap form.

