- □ When you return, obtain the ECG machine from the phlebotomy room and a gown from the closet (in rooms 2&4) or drawer under the exam table (rooms 3&5). Close the door blinds and draw the curtain by the exam bed. Have the participant change into the gown with their top clothes removed and the gown tied with the opening in front. Lie the participant down on the exam bed and then place the leads on the sternum and below the ribs and connect the ECG machine as trained. If you are not trained, [name], [name], or the study physician may complete the ECG.
- Once the participant is dressed and the ECG machine is retuned, you may EITHER 1) complete the NPI, FBI, and Zarit with the caregiver (preferred) or 2) move on and schedule a time within 3 days to complete these by phone or zoom. If completing in person, it is helpful to provide the response options (printed in a laminated sheet), and if completing virtually, you may email these to the caregiver in advance.
- □ Pay the study partner (\$20/visit hour, including from virtual visits + \$40 for transportation if relevant) and complete/sign a petty cash receipt.
- The clinician portion of the visit should be conducted LAST and will include the unblinding & planning for future care. Note that the study RA should remain blinded even after the participant completes the trial, so it is recommended for them to pay and say goodbye to the participant before the clinician visit, to avoid being accidentally unblinded.

Post-visit:

- Obtain any missing signatures
- □ Score cognitive testing & caregiver forms
- □ Check CALM website for posting of testing results
 - o sac-cu.org on internet explorer-- download "detailed results"
 - Copy the results into the "Safety Labs Template" file in dopamine>Lithium in FTD>Biological Samples, convert the results to numbers in excel (out of range results will highlight in pink), & print
- □ Obtain physician signature on lab results & ECG
- □ Count remaining pills & confirm with expected count. Once done, drop kit off at the NYSPI pharmacy for destruction.
- □ Enter data on REDCap
- Complete Serum-Sham Lithium level form, as described under Weeks 6/8.

Statistical Procedures and Data Analysis.

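### The week 12 compliance line expects 128 pills from four bottles, but the manual's own bottle size, pill strength and dose give 112

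*Combined protocol and SAP*

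**What the plan says.** The medication compliance item in the Week 12 Visit section reads "An additional 4 bottles (128 pills) should have been used since the week 8 visit", and the condition attached is "if the medication has been taken for 28 days at 600mg/day".

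The inputs to that count appear in three other places, all under Visit Checklists:

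- **Screening / Baseline, post-visit (study drug issue/return log):** "each kit contains 12 medication bottles. Each bottle contains 28 pills and is labeled by week". The same item adds "Each pill is 150mg of study drug" and says of the bottles needed between two visits that "when taking 450-600mg/day, they will need two".
- **Week 6, post-visit:** the top step is described as "increase dose to 600mg/day (two pills mornings, two pills evenings), using two new bottles". The Week 8 checklist gives the same split of pills.
- **Week 12, post-visit:** "Count remaining pills & confirm with expected count". The kit then goes to the pharmacy for destruction.

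**The concern.** A bottle count and a pill count in the same sentence should agree, and these do not. The 128 is also the only numerical expectation the manual gives for pill use in the last four weeks. The week 2, 6, 8 and 10 checklists remind the coordinator how many pills a bottle holds; the week 12 checklist does not. It asks only for agreement with an expected count.

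What is at stake is drug accountability at the final visit. A wrong reference value can raise a query about a patient who took every pill, or fail to raise one about a patient who used more than prescribed. After the kit is destroyed the pills cannot be recounted, and only the logged numbers remain.

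**Working it through.** **Inputs**

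- Pills per bottle: 28. Pill strength: 150 mg (Screening / Baseline checklist, drug log item).
- Dose and duration in the disputed line: 600 mg/day for 28 days; bottles: 4 (Week 12 Visit).
- Pills per day at 600 mg: 600 / 150 = 4, which agrees with the two-plus-two split in the Week 6 and Week 8 checklists.

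**Attempt to reproduce 128**

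- Bottle route: 4 bottles × 28 pills = 112.
- Dose route: 4 pills/day × 28 days = 112.
- Difference from the stated figure: 128 − 112 = 16 pills; 16 / 112 = 14.3% too high.

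Reaching 128 would take 128 / 4 = 32 pills per bottle, or 128 / 4 = 32 days of dosing, or 128 / 28 = 4.57 pills a day. None of these is in the manual. Bottles of 30 would give 120, which does not match either.

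**Do the manual's other counts fit 28 pills per bottle?**

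| Daily dose | Bottles per 14 days | Pills used in 14 days | Pills left | Manual's stated remainder |
|---|---|---|---|---|
| 150 mg | 1 (28 pills) | 14 | 14 | 14 (Week 2) |
| 300 mg | 1 (28 pills) | 28 | 0 | 0 (Week 4) |
| 450 mg | 2 (56 pills) | 42 | 14 | 14 in the second bottle (Weeks 6 and 10) |
| 600 mg | 2 (56 pills) | 56 | 0 | 0 in the second bottle (Week 8) |

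All of them fit. The week 12 figure is the only one that does not.

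**Effect on the returned count, if 128 were used as the benchmark**

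Take a patient who follows the full titration on schedule:

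- Kit contents: 12 × 28 = 336 pills.
- Use to week 12: 14 + 28 + 42 + 56 + 112 = 252. True return: 336 − 252 = 84.
- Return implied by 128: 336 − (14 + 28 + 42 + 56 + 128) = 336 − 268 = 68.

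The fully adherent patient returns 84 against an implied 68 and so appears to have missed 16 pills. A patient who used 16 extra pills would return 68 and match. Those 16 cannot come from the four assigned bottles, which hold only 112. They would have to come from the rest of the kit: two unassigned bottles (56 pills) and the leftovers from the 150 mg and 450 mg intervals (14 + 14), together 84.

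**The case against.** The arithmetic is not open to dispute; the consequences are. Four stronger readings are tempting, and the documents do not support them.

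**That full adherence is recorded as 87.5%.** A reader might infer this from 112 / 128. The manual defines no adherence percentage, formula or threshold. The drug log takes raw counts by named bottle: pills dispensed, then pills left over entered as returned. At 28 per bottle, four fully used bottles enter as 112 dispensed and 0 returned, and 128 is not an input. The week 12 checklist does not name 128 either, and it counts remaining pills rather than used ones. This objection stands.

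**That over-use would pass unnoticed.** Extra pills would have to come from bottles outside the four. Bottles are numbered, their use is logged visit by visit, and the whole kit is collected at week 12. An opened unassigned bottle or a changed leftover count could reveal the excess. Week 10 also has its own on-camera count, and its checklist tells the coordinator to work from 28 pills per bottle. This largely stands: over-use could match the stated total, but the documents do not show that it would escape detection.

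**That the treatment comparison is compromised.** The section on statistical procedures uses adherence in no model, covariate or analysis set, and the power statement does not depend on it. This objection stands in full.

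**That the line creates a dosing hazard.** Sixteen pills are 16 × 150 = 2,400 mg, or four days at the dose in that line. But the line tells nobody to take 128 pills. The count is made after the last visit, and no dosing decision during the trial is shown to rest on it.

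A careful coordinator could also recover 112 from the bottles, days and dose in the sentence itself. That makes harm less likely but does not make the number right. It remains the only stated pill-use figure for this check.

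**Conclusion.** The figure is wrong as written. By the manual's own numbers, expected use over 28 days at 600 mg/day is 112 pills, not 128, by two separate routes. The error is 16 pills, or 14.3% of the correct count, and it contradicts the four bottles in the same sentence.

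The practical effect is conditional. Only if staff use 128 as the expected count would a fully adherent patient appear 16 pills short, or 16 extra pills from elsewhere in the kit agree with the stated total. The documents do not show whether any patient was judged against 128. The 84 and 68 returned pills further assume that the patient followed the full titration on schedule; the 112 needs only the bottle size, pill strength, dose and days. The effect is confined to compliance recording and drug accountability. No planned analysis and no power figure changes.

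**What to change.** Reconcile the pill count in the Week 12 Visit compliance item with the bottle size and pill strength in the Screening / Baseline checklist. Those figures give 112 for the days and dose stated in the line. Nothing about the dose or schedule needs to change, and none is proposed.

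If any week 12 entries were judged against 128, recheck them from the dispensed and returned counts in the study drug log. Those raw counts do not depend on the 128, so the recheck does not need the destroyed kits. If no entry was judged that way, no recheck is needed.

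The cost is one number in the manual and, where it applies, a short review of logged counts.

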NCT02862210

Low-dose lithium for the treatment of behavioral symptoms in Frontotemporal Dementia Standard Operating Procedures Manual Version date 31May2021

Introduction

The Alzheimer's Drug Discovery Foundation funded a study titled "Low-dose lithium for the treatment of behavioral symptoms in Frontotemporal Dementia," which examines the efficacy and side effects of low dose lithium treatment for agitation/aggression/repetitive behaviors in 60 patients with FTD in a randomized, double blind, placebo-controlled 12-week trial.

Lithium carbonate or placebo will be started at an oral dose of 150 mg daily, with subsequent dose titration to 300mg/day at the 2-week visit, 450mg/day at the 4-week visit, and 600mg/day (maximum daily dose) at the 6-week visit. This upward dose titration will occur if clinically indicated, tolerated by the patient, and based on real/sham lithium blood level. An absence of response at lower doses without intolerable side effects is defined as clinically indicated. Assessments will take place at study entry (0 weeks), 2, 4, 6, 8, and 12 weeks, and the time-point of protocol exit for dropouts. Lithium levels will be drawn approximately 12-14 hours after the last dose.

Our primary outcome measures will be the Neuropsychiatric Inventory and the Clinical Global Impression scales.

Optimal target serum levels of lithium will be between 0.2 to 0.6 mmol/L due the risk of dropout due to lithium toxicity at higher levels. Clinical response of symptoms and side effects experienced by the patient will be primary in guiding oral lithium dose adjustment, and will override the information obtained from serum lithium levels if such a choice needs to be made.

This study will provide useful data on the efficacy and side effects of low-dose lithium treatment for FTD patients with symptoms of agitation/aggression, and possibly for other behavioral symptoms such as aberrant motor behaviors. The potential utility of lithium would provide an alternative for patients who show no/minimal response to or experience intolerable side effects while on antidepressants and antipsychotics.

During COVID, it was decided that the protocol would be updated to allow for a portion of the study visits to occur remotely. This was largely to reduce risks to participants once the study reopened (I.e. to minimize time traveling to a hospital), but also, we hoped this would make the study less burdensome to patients and study partners moving forward.

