While study staff is to remain blinded to drug assignment (lithium/placebo) during the 12 week trial, patients will have lithium blood levels taken at weeks (2, 4,) 6, 8, and 12 for safety monitoring and dosage adjustment. We will follow the procedures successfully used for blinded lithium levels in controlled trials in mood disorders. A physician independent of the study will receive lithium levels. This unblinded physician will provide the actual lithium level to the study physician for patients randomized to lithium, and make up a comparable sham level for patients on placebo. This sham level will vary from low to high levels and will be largely based on the number of pills taken by the patient. Target serum lithium level is 0.4 - 0.6 mmol/L. Based on the blood level received and clinical response and tolerability, the study physician will adjust the number of pills at study visits.

[name] will act as the unblinded RA. At each study visit where lithium levels are drawn (weeks 2,4,6,8,12) the study coordinator will give the serum lithium/sham lithium level form to the unblinded RA with the following information already filled in: current daily dose of lithium/placebo, how administered, number of hours between last oral dose and blood draw, date blood drawn. The unblinded RA will receive lab results for patients active in the protocol, including their real lithium level results, via the CALM website. The unblinded RA will email both the partially completed serum lithium/sham lithium level form, and that patient's lab results to the unblinded physician ([name]). The unblinded physician will complete the form by writing either a real lithium level or a sham lithium level and then signing and dating the form. At this time, the unblinded physician will also enter the real lithium/sham lithium level into the updated randomization spreadsheet provided to them by the NYSPI pharmacy. The unblinded physician will email the completed form to the unblended RA, who will forward it to the study coordinator

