Upon receipt of the completed serum lithium/sham lithium levels form, the study coordinator will contact the study physician and report: the sham/real lithium level, current daily dose, and study interval. Based on this information, as well as observed tolerability and side effects, the study physician will choose to change the patient's dosage or continue with current dosage. The study coordinator will then call the patient's caregiver to inform them of the dosing change or lack thereof. The study coordinator will log all of this information on the lithium/sham level log located in the front of the patient's research chart.

If there are unusual circumstances pertaining to dosage, such as a patient having skipped a dose the day before the blood draw, provide as much relevant information as needed to the unblinded physician so they may generate the most realistic sham level. Study coordinators and physicians should instruct caregivers to avoid administering study medication to a patient the same morning of a blood draw. We are targeting trough serum lithium levels for consistent measurement. If lithium is administered the same morning as a blood draw, the serum lithium level is likely to be artificially high and exceed our target therapeutic levels for this protocol. Caregivers can be instructed to give the lithium dose after the study visit.

Breaking the Blind and Open Treatment

Once all week 12 measures are completed, the study physician will break the blind with the participant and the study partner. The unblinding information is contained in an envelope provided by the research pharmacy, which must be requested and collected prior to the week 12 visit.

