5. If a patient cannot swallow the pills: If a patient is having difficulty swallowing the study medication capsules, a study physician can let the caregiver know that the lithium/placebo capsule can be opened and dissolved in applesauce or milk products such as yogurt. The NYSPI pharmacy has approved this procedure with these foods. Do not instruct caregivers to use any other foods without discussing with the lead site. The contents of the active and inactive capsules cannot be distinguished from each other when opened. Caregivers should be instructed to empty as much of the contents of the capsules into a small amount of food (1 tablespoon) and then stir the contents in before administering it to the patient. If this deviation from the protocol does occur, it will be filed as a protocol deviation for that patient.

Visit Checklists

These are item-by-item instructions for reference immediately before/during/after visits. Please refer to earlier sections of the manual for more details.

Screening / Baseline

Pre-visit:

- □ Complete instructions under "Scheduling Visits" section of manual
- Enter subject ID, date, and coordinator/physician initials on page 37 of the "Screening-Baseline INPERSON Packet" (dopamine>Lithium in FTD>Visit Instruments>In Person) & print double-sided. Also print visit schedule.
- Separate into the consent forms, clinician forms (which can be placed in a blue folder), and coordinator forms (kept however you like)
- □ Add paper MMSE, MDRS, and MDRS cards, response sheets (for FBI & Zarit), and copy of consent to coordinator materials
- Prepare & label blood tubes (1 red, 1 gold, 1 purple), petty cash + receipt booklet (\$20/visit hr payment + \$40 transportation payment if applicable)
- Add print names to consent forms where appropriate and mark signature lines with colored post-its (different color for each signer). Note that a study physician must be the "person obtaining consent". It is useful to clip the participant consent not staple so you can easily make photocopies once signed (one for the participant, one for Irving).
- Fill in as much demographic information as you can based on past research / clinical chart. If you are unsure of the accuracy of something, use pencil and confirm at visit.

During visit:

- Conduct consent. Arrange for the independent assessor of capacity to be present either during or immediately following the presentation of consent information. Give them all necessary forms.

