- Following the at-home blood draw, complete a Serum Sham Lithium Level Form (dopamine>Lithium in FTD>Serum-Sham Lithium Levels) and send it to [name], who will send the form to [name] along with the REAL serum lithium level (once it is available on CALM). [name] will then complete the form and send it back to [name], who will send it to you. Save the signed form in a unique subject folder in dopamine>Lithium in FTD>Serum-Sham Lithium Levels.
- If no contradictions per study clinician, AND serum lithium/sham level is within the target window, instruct participant/study partner to stay at OR increase dose to 600mg/day (two pills mornings, two pills evenings), using two new bottles.
- □ Obtain clinician signature on REDCap study drug issue/return log, resolve any missing data from clinician forms, fill out serum-sham lithium level REDCap form.
- □ Schedule Week 10 visit with participant for 2 weeks after their week 2 visit.
- □ If not already done, schedule in-person week 12 visit and submit room request to Irving

Week 10

Note: there is no blood draw associated with this visit unless the medication dose was increased at week 8. If this is the case, follow instructions related to at-home blood draws & serum/sham lithium levels.

Pre-visit:

- □ Create zoom link & send along with date/time of visit & visit schedule to the study partner
- □ Send a calendar invitation to the study physician. In the calendar invitation, include:
 - o Zoom link
 - o Links to clinician forms within REDCap for the correct subject/week
 - o List of clinician forms: Treatment emergent symptoms, CGI-Severity, CGI-Change
 - o Current subject medication dose & any other relevant information

During visit:

- □ Complete medication compliance check: have study partner count pills remaining in the bottle they have been using. Each bottle contains 28 pills, so calculate the number of pills that should be remaining based on dose & time since the last visit.
- On REDCap, complete the following forms with the study partner:
 - Visit registry, concomitant meds, NPI, Stereotypic/Ritualistic behaviors, study drug issue/return log

Post-visit:

- □ Instruct participant/study partner to stay at current dose, using two new bottles.
- Obtain clinician signature on REDCap study drug issue/return log, resolve any missing data from clinician forms.

Week 12

Pre-visit:

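### The manual gives two lower bounds for the target lithium window (0.2 and 0.4 mmol/L), and the week-6 and week-8 conditions for 600 mg/day do not say which applies

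*Combined protocol and SAP*

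**What the plan says.** The manual (version date 31 May 2021) states the target window twice.

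- *Introduction*: "Optimal target serum levels of lithium will be between 0.2 to 0.6 mmol/L due the risk of dropout" from toxicity at higher levels.
- *Blinding: Lithium/sham levels procedures*: "Target serum lithium level is 0.4 - 0.6 mmol/L".

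The window is then used, without numbers, in two dosing steps.

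- *Visit Checklists*, Week 6, Post-visit: if the study clinician has no objection, "AND serum lithium/sham level is within the target window, instruct participant/study partner to increase dose to 600mg/day".
- *Visit Checklists*, Week 8, Post-visit: the same opening, then "AND serum lithium/sham level is within the target window, instruct participant/study partner to stay at OR increase dose to 600mg/day".

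The checklists open with a pointer: "Please refer to earlier sections of the manual for more details".

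Other clauses bear on how much weight the level carries. The *Introduction* makes response and side effects the main guide to dose and says that they "will override the information obtained from serum lithium levels if such a choice needs to be made". The blinding section says: "Based on the blood level received and clinical response and tolerability, the study physician will adjust the number of pills at study visits". It adds, once the coordinator has reported the level: "Based on this information, as well as observed tolerability and side effects, the study physician will choose to change" the dose or keep it. The *Week 6 Visit* and *Week 8 Visit* sections list the blinded level as one of three considerations, beside response and side effects, and give no window.

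**The concern.** A numeric threshold that enters a dosing step should have one value. Here it has two, and the checklists that apply it name neither. Their pointer to the earlier sections does not help, because those sections contain both values.

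Two coordinators or physicians could read the same level differently in good faith. Sham levels pass through the same step, so this can happen in either arm. Two other things are at stake:

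- **Reporting.** Achieved levels and doses are logged for each participant and can be reported. A report cannot state one planned target window from this manual.
- **Handover.** *Breaking the Blind and Open Treatment* asks that outside physicians be told the target levels for this population, again without numbers. Staff could pass on either window.

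**Working it through.** No stated power or sample-size figure bears on this point, so there is none to reproduce. The check sets the passages side by side and uses simple arithmetic.

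**Inputs**

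| Source | Lower bound (mmol/L) | Upper bound (mmol/L) |
|---|---|---|
| Introduction | 0.2 | 0.6 |
| Blinding: Lithium/sham levels procedures | 0.4 | 0.6 |
| Week 6 and Week 8 checklists | not given | not given |

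**Widths** (upper minus lower)

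- Introduction: 0.6 − 0.2 = 0.40 mmol/L
- Blinding section: 0.6 − 0.4 = 0.20 mmol/L
- Band in dispute: 0.40 − 0.20 = 0.20 mmol/L
- Share of the Introduction's window in dispute: 0.20 / 0.40 = 0.50
- Difference in upper bounds: 0.6 − 0.6 = 0

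**Result of the checklist condition by level**

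| Real or sham level (mmol/L) | Introduction window | Blinding-section window | Agree? |
|---|---|---|---|
| below 0.20 | not met | not met | yes |
| 0.20 to just under 0.40 | met | not met | **no** |
| 0.40 to 0.60 | met | met | yes |
| above 0.60 | not met | not met | yes |

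A reported level of 0.30, for example, meets the condition under the Introduction and fails it under the blinding section.

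**Does any other text settle it?**

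1. The Introduction calls its range optimal and the blinding section does not use that word. Nothing defines two separate ranges, and the range called optimal is the wider one, so it does not read as a preferred zone inside a broader target.
2. The blinding section's advice on dosing the morning of a draw, and the section on breaking the blind, mention target therapeutic levels without numbers.
3. The override and the physician's decision rank the level against other information. They do not say which window is meant, and the checklists do not repeat them.
4. The Week 6 and Week 8 Visit sections treat the level as one consideration, while the checklists word it as a joint condition. That is a second difference to reconcile.

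The 0.50 share describes the width of an interval. It is not a share of participants or decisions: the documents give no distribution of levels, so that number cannot be computed.

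**The case against.** The strongest reply accepts the mismatch and disputes its consequence.

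- **The window may work only as a ceiling.** The reason given for the range is toxicity at higher levels, and the advice on the timing of blood draws is also about levels that come out too high. On that reading only the 0.6 bound matters, and it agrees. This would remove the effect on the 600 mg/day step, but it departs from the plain wording, which requires the level to be inside a window. The manual does not say that only the upper bound counts.
- **The level is subordinate.** Response and side effects outrank it, and the visit sections list it as one consideration of three. This stands, and it is why the effect is described as possible rather than certain. It does not choose a window, and the checklists still word the level as a condition.
- **The coordinator does not decide the dose.** The physician chooses after hearing the level, and the checklist is a later step. This also stands. However, the physician has the same two windows to work from.
- **No planned analysis uses the level.** Dosing is flexible, the analysis is intent-to-treat, and serum lithium is not an outcome or covariate in *Statistical Procedures and Data Analysis*. This is correct, and it limits the point to conduct and reporting.

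**Conclusion.** The concern holds. Two current sections give different lower bounds for one target, and two dosing steps rely on that target without a number. Levels from 0.20 to just under 0.40 mmol/L are classified in opposite ways; all other levels are classified alike.

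The conclusion rests on reading the checklist condition as two-sided, which is its plain meaning. It needs no pharmacokinetic or distributional assumption. The textual contradiction is certain. Its effect on actual dosing is possible and cannot be sized from the documents. No bias between arms is claimed, and no planned test is affected. It should be corrected because the threshold enters dose adjustment, and the blinding section says that levels are drawn for that purpose and for safety.

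**What to change.** 1. Reconcile the *Introduction* and *Blinding: Lithium/sham levels procedures* so that one window is stated throughout. Which window is right is for the investigators to decide.
2. Cite that window by number in the Week 6 and Week 8 Post-visit checklists.
3. State in both checklists how the Introduction's override and the physician's decision apply to the condition, and bring this into line with the Week 6 Visit and Week 8 Visit sections.

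The cost is wording in a few places and a note to staff. No power, alpha or sample-size figure changes.
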